PSRT	Protocol Safety Review Team
Q	Inter-compartmental clearance
QA	quality assurance
RSC	Regulatory Support Center
SAE	serious adverse event
SC	Subcutaneous
SHIV	simian-human immunodeficiency virus
SST	serum separator tube
TCR	tissue cross reactivity
T _½	half-life
Tmax	time of maximal concentration (C _{max})
UNAIDS	Joint United Nations Programme on HIV/AIDS
UP	unanticipated problem
USP	United States Pharmacopeia
V _d	volume of distribution
VRC	Vaccine Research Center
WBC	white blood cell

PRÉCIS

VRC 605: A Phase 1 Dose-Escalation Study of the Safety and Pharmacokinetics of a Human Monoclonal Antibody, VRC-HIVMAB075-00-AB (VRC07-523LS), Administered Intravenously or Subcutaneously to Healthy Adults

Study

Design:

This is the first study in healthy adults of the VRC-HIVMAB075-00-AB (VRC07-523LS) monoclonal antibody (MAb). It is a dose-escalation study to examine safety, tolerability, dose, and pharmacokinetics of VRC07-523LS. The hypothesis is that VRC07-523LS administration to healthy adults will be safe by the intravenous (IV) and subcutaneous (SC) routes. A secondary hypothesis is that VRC07-523LS will be detectable in human sera with a definable half-life.

Product

Description: VRC-HIVMAB075-00-AB (VRC07-523LS) is a human MAb targeted to the HIV-1 CD4 binding site. It was developed by the VRC/NIAID/NIH and manufactured under current Good Manufacturing Practice regulations at the VRC Pilot Plant operated under contract by the Vaccine Clinical Materials Program, Leidos Biomedical Research, Inc., Frederick, MD. Product is provided at 100 ± 10 mg/mL in a volume of 6.25 ± 0.10 mL filled into 10 mL glass vials.

Subjects: Healthy adults, 18-50 years of age.

Study Plan: This study includes 4 open-label, dose escalations of VRC07-523LS from 1 mg/kg IV to 40 mg/kg IV, 1 route escalation from IV to SC, and 2 open-label groups to assess repeat dosing of VRC07-523LS. Groups will be enrolled per the dose and route escalation and safety evaluation plan.

VRC 605 Study Schema					
Group	Subjects	Administration Schedule			
		Day 0	Week 12	Week 24	
1	3	1 mg/kg IV			
2	3	5 mg/kg IV			
3	3	5 mg/kg SC			
4	3	20 mg/kg IV			
5	3	40 mg/kg IV			
6	5	5 mg/kg SC	5 mg/kg SC	5 mg/kg SC	
7	5	20 mg/kg IV	20 mg/kg IV	20 mg/kg IV	
Total*	25	*The expected enrollment is 25 subjects. Enrollment up to a total of 40 subjects is permitted if additional subjects are necessary for safety or PK evaluations.			

Study Duration: Subjects will be followed for 24 weeks after the last study product administration.

1. INTRODUCTION

The global incidence of new human immunodeficiency virus (HIV) infection peaked in the mid-1990s. The incidence of new infections in 2014 is reported by Joint United Nations Programme on HIV/AIDS (UNAIDS) as 2 million new cases, a reduction of 35% since 2000, with an estimated global total of 36.9 million people living with HIV [1]. The decrease in HIV incidence, due to multiple factors including prevention and treatment programs, is an encouraging trend but the scope and cost of the epidemic remains a global health threat.

The National Institute of Allergy and Infectious Diseases (NIAID), National Institutes of Health (NIH) is committed to the development of safe, effective methods to prevent and treat HIV and AIDS worldwide. In this regard, the Vaccine Research Center (VRC), NIAID and Division of AIDS (DAIDS), NIAID, are collaborating to evaluate the potential clinical uses of HIV-specific broadly neutralizing human monoclonal antibodies (MAb) [2-4].

The VRC, NIAID, NIH has developed VRC07-523LS, a highly potent and broadly neutralizing HIV-1 human MAb targeted against the HIV-1 CD4 binding site. A similar antibody, VRC01 MAb, is currently in clinical trials under IND 113,611 [prevention indication] and IND 126,001 and IND 126,664 [therapeutic indication], was originally discovered in a subject infected with HIV-1 for more than 15 years and whose immune system controlled the virus without anti-retroviral therapy [5]. Through advances in B-cell immunology, cloning and structure-guided optimization techniques, numerous HIV-1 neutralizing MAbs, including VRC07 (“07” denotes sequential numbering when discovered), VRC07-523 (“523” denotes sequential numbering when engineered variant generated), and later VRC07-523LS (“LS” denotes 2 amino acid mutations), were isolated with potency and breadth greater than those of early antibodies[3].

The VRC07 (wild-type) heavy chain was identified by 454 deep sequencing based on its similarity to the VRC01 MAb and paired with the VRC01 (wild-type) light chain. The mutations that together define the 523 designations are a glycine to histidine mutation at residue 54 of the heavy chain, a deletion of the first two amino acids, glutamate and isoleucine, from the light chain, and a valine to serine mutation at the third amino acid residue of the light chain. The LS designation specifies methionine to leucine (L) and asparagine to serine (S) (M428L/N434S, referred to as LS) changes within the C-terminus of the heavy chain constant region. The LS mutation was introduced by site-directed mutagenesis to increase the binding affinity for the neonatal Fc-receptor (FcRn), resulting in increased recirculation of functional IgG [6, 7], thus increasing plasma half-life.

VRC-HIVMAB075-00-AB (VRC07-523LS) is an investigational drug that has not been administered to humans prior to this study. VRC07-523LS is intended for the prevention of HIV-1 infection in healthy adults initially. VRC07-523LS may also be evaluated for prevention of mother-to-child transmission and for treatment of HIV-1 infected subjects.

1.1 RATIONALE FOR THE STUDY

VRC's clinical development plans for neutralizing MAbs include potential uses in three broad areas: 1) prevention of mother-to-child transmission (MTCT) of HIV, 2) prevention of sexual transmission of HIV, and 3) therapeutic application in HIV-1 infected individuals. The initial development plan focused on clinical research to lead to an efficacy evaluation of VRC01 for MTCT of HIV. To evaluate the safety of administering VRC01 to infants who may be HIV-infected at birth, studies in infants were preceded by Phase 1 trials in HIV-infected adults (VRC 601) and HIV-uninfected adults (VRC 602) that began in 2013 and 2014, respectively.

VRC01 has been assessed as safe and well tolerated at the 5-40 mg/kg doses administered intravenously (IV) and at 5 mg/kg subcutaneously (SC) in both HIV-infected and HIV-uninfected adult populations. The pharmacokinetic (PK) parameters of passively administered VRC01 were also evaluated. For healthy adults who received VRC01 at the 5-40 mg/kg doses administered IV (n=18), the clearance was 0.016 ± 0.003 L/h and an overall mean value for the elimination half-life was 15.4 ± 3.9 days for IV administration. At 5 mg/kg SC (n=5), the clearance was 0.029 ± 0.007 L/h, and the mean elimination half-life was 16.6 ± 2.9 days. Work is ongoing to further describe the PK and biological activity of VRC01 after repeat dosing in HIV-infected and -uninfected adults.

VRC07-523LS, an engineered variant of VRC07 that was discovered in the same HIV-1 infected subject as VRC01, neutralizes more HIV envelope strains than VRC01 at lower concentrations.

VRC07-523LS was found to be 5-to 8-fold more potent than VRC01, with an inhibitory concentration $IC_{50} < 50$ mcg/mL against 96% of HIV-1 pseudoviruses representing the major circulating HIV-1 clades and $IC_{50} < 1$ mcg/mL against 92% of HIV-1 viruses tested and displayed minimal levels of autoreactivity. VRC07-523LS was shown to have a prolonged half-life over VRC07 by about 2-fold [3].

In vivo proof-of-concept studies showed that VRC07-523LS is about 5-fold more potent than VRC01LS in Rhesus macaques and displays a longer half-life (9.8 days) than VRC07 (4.9 days) after a single dose of MAb at 10 mg/kg administered IV [3].

When administered IV at a single dose of 10 mg/kg in cynomolgus macaques, the half-life of VRC07-523LS was about 12 days, and persisted at least 28 days (last collection point) in rectal and vaginal secretions and tissues. When administered SC at a single dose of 10 mg/kg in rhesus macaques, the half-life of VRC07-523LS was about 14 days and it persisted at least 49 days (last collection point) in rectal, vaginal and nasal secretions. Complete protection from SHIV-SF162P3 challenge was demonstrated with a single dose of VRC07-523LS at 20 mg/kg administered IV.

A repeat dose IV and SC toxicity study with VRC07-523LS was performed in male and female Sprague-Dawley rats in accordance with “Good Laboratory Practice (GLP) for Nonclinical Laboratory Studies.” Treatment with VRC07-523LS at doses up to 400 mg/kg/dose IV or 40 mg/kg/dose SC with three doses at 10 days intervals was generally well tolerated as most findings were reversible and no longer seen at the end of the recovery period. Additionally, histologic changes were not observed in the GLP repeat dose toxicology study in the cell types with staining observed in the GLP tissue cross reactivity (TCR) study.

Increased neutralization potency *in vitro* and prolonged half-life of VRC07-523LS correlate with improved protection against SHIV infection *in vivo* in animal studies, suggesting a potential clinical application against HIV-1 infection in humans in preventive and/or therapeutic settings.

The proposed VRC07-523LS doses are based on human studies of VRC01, preclinical studies of VRC07-523LS and the requirements to assess PK at a range of doses that will allow for full PK analysis and predictive modeling. This range of doses allows for informative PK modeling to be performed with the study data obtained here. Preclinical studies with VRC07-523LS to date also support the proposed human doses and intervals between doses to achieve passive immunity as described in Section 2 and in the Investigator’s Brochure (IB).

1.2 VRC07-523LS SPECIFIC LABORATORY ASSESSMENTS

Laboratory assessments in this Phase 1 study of VRC07-523LS include PK parameters, development of anti-VRC07-523LS antibody following exposure to the product, and functional capacity (neutralization) of the MAb following infusion.

VRC07-523LS concentration for the PK analysis in this Phase 1 study will be measured by an ELISA on a Beckman Biomek based automation platform. The monoclonal antibody 5C9 is coated onto Immulon-4HXB microtiter plates overnight at 4° C at a concentration of 3.5 mg/mL. Plates are washed and blocked (10% FBS in PBS) for 2 hours at room temperature. Duplicate serial 3-fold dilutions covering the range of 100 - 24300 of the test sample are incubated 2 hours at 37° C followed by Horseradish Peroxidase - labeled goat anti-human antibody (1hour, 37° C), and TMB substrate (15 minutes, room temperature). Color development is stopped by addition of sulfuric acid and plates are read within 30 minutes at 450 nm via the Molecular Devices Paradigm plate reader. Four parameter logistic curve regression of a standard curve of VRC07-523LS covering the range from 0.98 to 1000 ng/mL is utilized to quantitate the sample concentrations based upon the average of sample dilutions within the range of the assay.

Assessment for development of anti-VRC07-523LS antibodies in subjects will be performed using the Meso Scale Discovery (MSD) platform based on electrochemiluminescence. The developed ADA assay uses the biotin-labeled VRC07 immobilized on a streptavidin-coated MSD plate as the capture molecule, and the SULFO-TAG labeled VRC07 as the reporter molecule. This assay is independent of the anti-VRC07-523LS antibody isotype, and permits the detection of both high and low affinity antibodies. Evaluation for anti-VRC07-523LS antibodies will be conducted in batches, on samples collected at 4 weeks after each antibody administration. Samples collected at other visits could be tested if there is a clinical indication or a decrease in PK values observed.

Depending upon the concentrations measured in collected specimens, further evaluation of the research samples to assess for functional capacity to neutralize HIV may be conducted by an *in vitro* cell-based virus neutralization assay using the pseudotyped viruses [8-10].

As an exploratory evaluation, subjects may be evaluated for their IgG1 allotypes to determine the potential for theoretical allotype-specific effects on the VRC07-523LS pharmacokinetics such as reduced half-life or anti-drug antibody response [11-13]. Coded stored samples will be used for evaluation of the genetic sequence of the immunoglobulin heavy chain constant region allotype.

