3.2 SECONDARY OBJECTIVES

- To evaluate the pharmacokinetics of VRC-HIVMAB075-00-AB at each dose level through 24 weeks after the last dose.
- To determine whether anti-drug antibody (ADA) to VRC07-523LS can be detected in recipients of VRC-HIVMAB075-00-AB.

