4. STUDY DESIGN

This is an open-label, dose-escalation study to examine the safety, tolerability, dose, and PK of VRC07-523LS in healthy adults. The hypothesis is that VRC07-523LS administration will be safe by the IV and SC routes. The secondary hypothesis is that VRC07-523LS will be detectable in human sera with a definable half-life. The study schema is shown in Table 3.

Table 3: VRC 605 Study Schema

Group	Subjects	Administration Schedule		
		Day 0	Week 12	Week 24
1	3	1 mg/kg IV		
2	3	5 mg/kg IV		
3	3	5 mg/kg SC		
4	3	20 mg/kg IV		
5	3	40 mg/kg IV		
6	5	5 mg/kg SC	5 mg/kg SC	5 mg/kg SC
7	5	20 mg/kg IV	20 mg/kg IV	20 mg/kg IV
Total*	25	*The expected enrollment is 25 subjects. Enrollment up to a total of 40 subjects is permitted if additional subjects are necessary for safety or PK evaluations (Section 4.3).		

Enrollment will begin in the 1 mg/kg IV dose group (Group 1). Enrollments into the subsequent dose and route groups may proceed after dose and route escalation reviews (Section 4.3). Subjects in Groups 1 through 5 will be expected to be available for follow-up visits during 24 weeks of study participation; subjects in Groups 6 and 7 will be expected to be available for follow-up visits during 48 weeks of study participation

For each new dose level (1 mg/kg, 5 mg/kg, 20 mg/kg and 40 mg/kg) and for the initial SC group, following the first product administration, the study team will wait at least 2 days before administering VRC07-523LS to a second subject within the same group. Safety review decisions and the status of the enrollment process will be transparent to the Protocol Safety Review Team (PSRT) throughout the trial and discussed during the weekly safety review.

Safety laboratory samples will be collected throughout the study as per the Schedule of Evaluations. Subjects will keep a daily diary of solicited systemic symptoms for 3 days after each product administration. PK samples will be collected at specified intervals through 24 weeks after a subject's last product administration.

When the subject agrees, optional oral samples will be collected at specified intervals for the purpose of detecting if measurable levels of VRC07-523LS can be found in oral mucosa.

The study will be conducted by the VRC Clinical Trials Program at the NIH Clinical Center (NIH CC).

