Table 5 gives the upper and lower bounds for 95% exact binomial confidence intervals for all possible number of observed events within a group. Within the group of size n=3, if no subjects experience the event, the 95% exact 2-sided confidence interval for the true rate has upper bound as 0.708; if all subjects experience the event, the 95% exact 2-sided confidence interval for the true rate has lower bound as 0.292. Within the group of size n=5, if no subjects experience the event, the 95% exact 2-sided confidence interval for the true rate has upper bound as 0.522; if all subjects experience the event, the 95% exact 2-sided confidence interval for the true rate has lower bound as 0.478.

Table 5: 95% Confidence Intervals of the True Rate for All Possible Number of Observed Events within a Group

Within a group (n=3) 95% confidence interval			Within a group (n=5) 95% confidence interval		
Observed rate	Lower bound	Upper bound	Observed rate	Lower bound	Upper Bound
0/3	0	0.708	0/5	0	0.522
1/3	0.008	0.906	1/5	0.005	0.716
2/3	0.094	0.992	2/5	0.053	0.853
3/3	0.292	1	3/5	0.147	0.947
			4/5	0.284	0.995
			5/5	0.478	1

Tables 4 and 5 apply to the secondary and exploratory endpoints as well.

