6.4 STATISTICAL ANALYSIS

6.4.1 Analysis Variables

The analysis variables consist of baseline variables, pharmacokinetics and safety variables for primary and secondary objective analyses.

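### Anti-drug antibody is routinely tested only 4 weeks after each dose; adding the Day 0 and final-visit sera already scheduled would supply a baseline and cover the untested last 20 weeks

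*Combined protocol and SAP*

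**What the plan says.** Section 3.2 makes ADA a secondary objective: "To determine whether anti-drug antibody (ADA) to VRC07-523LS can be detected in recipients of VRC-HIVMAB075-00-AB". Section 1.2 lists among the laboratory assessments "development of anti-VRC07-523LS antibody following exposure to the product".

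The routine timing is in Section 1.2: "Evaluation for anti-VRC07-523LS antibodies will be conducted in batches, on samples collected at 4 weeks after each antibody administration". The next sentence gives the only provision for other times: "Samples collected at other visits could be tested if there is a clinical indication or a decrease in PK values observed". The same section describes the assay, with "the biotin-labeled VRC07 immobilized on a streptavidin-coated MSD plate as the capture molecule" and labelled VRC07 again as the reporter.

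Section 6.4.1 states that "The analysis variables consist of baseline variables, pharmacokinetics and safety variables for primary and secondary objective analyses". ADA is not named there or elsewhere in Section 6.4, and Appendix III has no ADA row. Section 6.3.2 nevertheless extends the precision tables to this endpoint: "Tables 4 and 5 apply to the secondary and exploratory endpoints as well". PK follow-up runs longer than routine ADA testing. Section 4 says "PK samples will be collected at specified intervals through 24 weeks after" the last administration.

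**The concern.** There are three gaps, in decreasing order of certainty.

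1. **No planned baseline.** Development after exposure means a change from the pre-dose state. If a subject's first result, at week 4, is positive, the plan has no pre-dose result beside it and no rule for classing it. A positive ADA result is not among the listed reasons for testing another sample. In Groups 6 and 7 an earlier on-study negative can serve as reference for a later positive, so there the gap concerns the first result only.

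2. **No routine test late in follow-up.** After the 4-week sample that follows the last dose, ADA is tested only if someone acts on a clinical or PK signal, and no PK threshold is given. ADA that arises later without such a signal would be missed.

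3. **Possible masking at week 4.** Capture and reporter are both labelled VRC07, so circulating drug could compete for ADA. This is most plausible in the 11 subjects on 20 or 40 mg/kg (Groups 4, 5 and 7: 3 + 3 + 5). It is possible, not shown, because the documents do not state the assay's drug tolerance.

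At stake is how far the ADA result can be interpreted in groups where one subject shifts the estimate by a third or a fifth.

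**Working it through.** **The plan's own figures.** Table 5 reproduces as exact (Clopper–Pearson) intervals. For 0/n the upper limit is 1 − 0.025^(1/n): 0.708 for n = 3 and 0.522 for n = 5. For 1/3 the interval is 0.008–0.906, and for 1/5 it is 0.005–0.716. All match.

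**Coverage** (study days from Appendix III).
- Groups 1–5: one routine test at day 28, follow-up to day 168. (168 − 28)/7 = 20 weeks.
- Groups 6–7: routine tests at days 28, 112 and 196, follow-up to day 336. (336 − 196)/7 = 20 weeks.
- Planned routine assays: 15 × 1 + 10 × 3 = 45.

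**Chance that a baseline matters.** The documents give no prevalence p of pre-existing reactivity, so p is assumed. The chance of at least one reactive subject among n is 1 − (1 − p)^n.

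| Assumed p | n = 3 | n = 5 | All 25 |
|---|---|---|---|
| 1% | 3% | 5% | 22% |
| 2% | 6% | 10% | 40% |
| 5% | 14% | 23% | 72% |

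One such subject counted as developed ADA moves 0/3 (0–0.708) to 1/3 (0.008–0.906), or 0/5 (0–0.522) to 1/5 (0.005–0.716).

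**Drug present at week 4 and at the final visit** (illustration for the third gap). Section 1.1 gives VRC01 clearance of 0.016 L/h and half-life of 15.4 days after IV dosing. Volume V = 0.016 × 24 × 15.4 / ln 2 = 8.53 L. With an assumed 70 kg subject and one compartment, C(t) = dose × 70 / V × 2^(−t/half-life), at t = 28 and 168 days. V is held fixed while the half-life varies: 12 days (this product in cynomolgus macaques, Section 1.1), 15.4 days (human VRC01), 30.8 days (assumption: the two-fold macaque ratio of VRC07-523LS to VRC07, applied to human VRC01) and 40 days (assumption). Group 7 sums the doses at days 0, 84 and 168. Levels are in mcg/mL, early → late.

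| | 12 d | 15.4 d | 30.8 d | 40 d |
|---|---|---|---|---|
| 5 mg/kg IV, week 4 → 24 | 8 → 0.003 | 12 → 0.02 | 22 → 0.9 | 25 → 2.2 |
| 20 mg/kg IV, week 4 → 24 | 33 → 0.01 | 47 → 0.09 | 87 → 3.7 | 101 → 8.9 |
| 40 mg/kg IV, week 4 → 24 | 65 → 0.02 | 93 → 0.17 | 175 → 7.5 | 202 → 18 |
| Group 7, week 28 → 48 | 33 → 0.01 | 48 → 0.09 | 103 → 4.4 | 130 → 11.5 |

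The fall over the 140 days is 2^(140/half-life): 3251-, 545-, 23.4- and 11.3-fold. Section 6.4.5 anticipates two compartments, so these levels may be too high. They compare drug load at two times and do not demonstrate interference. No SC levels were computed.

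**Availability of serum** (Appendix III). In all four schedules the Day 0 pre-dose total is 27 mL = 3 (blood count) + 4 (chemistry) + 4 (PK) + 16 (serum). The last step in cumulative volume is 418 − 398, 422 − 402, 708 − 688 and 719 − 699, each 20 mL = 4 (PK) + 16 (serum). The table columns are broken in the available text, so the Day 0 placement is inferred from column order and these totals. Pre-dose serum of 24 mL is also drawn at screening and again at enrollment. The row is general research serum; no aliquot is reserved for ADA.

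**The case against.** The strongest reply is that nothing is lost. Section 3.2 asks only whether ADA can be detected, and testing after every dose addresses that. Pre-dose serum is stored, Section 7.9.1 permits its use for protocol-related immunology evaluations, and the optional-testing sentence does not forbid checking Day 0 after a positive. That is correct: the first gap is recoverable. But nothing requires the check or says how its result would be classed, and a rule fixed beforehand avoids selective testing afterwards.

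The prevalence range is assumed, and exclusion criterion 1 bars prior monoclonal antibody recipients, which may lower it. That stands, as does the point that the chance for any one group (3% to 23% in the table) is much smaller than for all 25 subjects. Masking, if present, would also tend to hide pre-existing reactivity at week 4, so the first and third gaps partly offset each other.

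PK is analysed subject by subject through 24 weeks after the last dose, and this is a real partial safeguard for late ADA. What remains is ADA without a PK or clinical signal. The masking argument is unproven, and the first two gaps do not need it.

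**Conclusion.** The concern holds, as an inexpensive improvement to a secondary endpoint and not as an error in any stated figure. The absence of a planned baseline and the 20 weeks without a routine test in every group follow directly from Section 1.2 and Appendix III, with no assumption. Fifteen of 25 subjects have a single routine ADA result. The 22% / 40% / 72% chance that pre-existing reactivity occurs somewhere in the trial rests on an assumed prevalence of 1% / 2% / 5%. The lower drug load at the final visit, 11-fold or more in every IV scenario, rests on the one-compartment illustration; whether drug actually interferes depends on a drug tolerance that is not stated. No primary safety conclusion is affected. The change should be made.

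**What to change.** In Section 1.2, keep the 4-week samples and add to routine ADA testing, in all groups, the Day 0 pre-dose serum and the final-visit serum (week 24 for Groups 1–5, week 48 for Groups 6–7). In Section 6.4, define treatment-emergent ADA relative to Day 0, and report each ADA result with the drug concentration in that sample and the assay's drug tolerance.

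Cost: 2 × 25 = 50 assays on top of 45, for a total of 95; at the permitted maximum of 40 subjects, 2 × 40 = 80 would be added. No visit or blood draw is added, but an ADA aliquot should be reserved from the research serum. The limitation is residual drug in the final samples, up to about 18 mcg/mL at 40 mg/kg and 11.5 mcg/mL in Group 7 if the half-life is 40 days. Any interference would be reduced, not removed.

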3. STUDY OBJECTIVES

3.1 PRIMARY OBJECTIVES

- To evaluate the safety and tolerability of VRC-HIVMAB075-00-AB administered as a single dose at 1 mg/kg IV, 5 mg/kg IV, 20 mg/kg IV, 40 mg/kg IV, and 5 mg/kg SC to healthy adults.
- To evaluate the safety and tolerability of VRC-HIVMAB075-00-AB administered at 20 mg/kg IV by repeat dosing every 12 weeks for a total of 3 infusions to healthy adults.
- To evaluate the safety and tolerability of VRC-HIVMAB075-00-AB administered at 5 mg/kg SC by repeat dosing every 12 weeks for a total of 3 injections to healthy adults.

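### Routine ADA testing is confined to 4-week samples, where remaining drug could mask ADA in a bridging assay and more so at higher doses; no low-drug sample or rule for a valid negative is planned

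*Combined protocol and SAP*

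**What the plan says.** Section 3.2 sets the secondary objective: "To determine whether anti-drug antibody (ADA) to VRC07-523LS can be detected in recipients of VRC-HIVMAB075-00-AB". Section 1.2 gives the assay format, which "uses the biotin-labeled VRC07 immobilized on a streptavidin-coated MSD plate as the capture molecule, and the SULFO-TAG labeled VRC07 as the reporter molecule". It then fixes the routine test time: "Evaluation for anti-VRC07-523LS antibodies will be conducted in batches, on samples collected at 4 weeks after each antibody administration". In Groups 6 and 7 that means weeks 4, 16 and 28. The next sentence adds an option: "Samples collected at other visits could be tested if there is a clinical indication or a decrease in PK values observed".

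Section 1.2 gives no drug concentration up to which a negative result is valid, and it does not mention sample pre-treatment for this assay. Section 6.4.1 lists baseline, pharmacokinetic and safety variables, and Section 6.4 has no ADA analysis. Section 6.3.2 nevertheless extends Tables 4 and 5 to the secondary endpoints, so ADA counts would be read against those tables.

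**The concern.** In a bridging assay, ADA gives a signal only when one ADA molecule binds a capture copy and a reporter copy of the labelled antibody. Unlabelled VRC07-523LS in the same serum can occupy those binding arms and prevent the bridge. The product is engineered for a long half-life, so a good deal of it can be expected to remain at 4 weeks.

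A week-4 negative therefore has two readings, no ADA or ADA hidden by drug, and the plan has no rule to separate them. Because drug level rises with dose, the groups given 20 and 40 mg/kg are the ones whose negatives are least secure. If all negatives are counted alike, a 0/5 in Group 7 would be given the Table 5 upper bound of 0.522, which is correct only if all five negatives are real.

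**Working it through.** **No figure of the plan's own.** The documents state neither a human week-4 concentration of VRC07-523LS nor an ADA drug tolerance. Tables 4 and 5 were recomputed as a side check and agree within rounding in the last digit.

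**Inputs**
- Doses from Section 3.1: "single dose at 1 mg/kg IV, 5 mg/kg IV, 20 mg/kg IV, 40 mg/kg IV, and 5 mg/kg SC to healthy adults".
- VRC01 IV in healthy adults, Section 1.1: "the clearance was 0.016 ± 0.003 L/h and an overall mean value for the elimination half-life was 15.4 ± 3.9 days for IV administration". VRC01 at 5 mg/kg SC, same section: 0.029 L/h and 16.6 days.
- Half-life gain: Section 1.1 reports about 2-fold over VRC07. Applying 1- to 2-fold to the VRC01 human half-life is an assumption.
- Body weight: 70 kg assumed. Only the 115 kg cap is in the documents; 50 to 115 kg is shown as a range.

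**Volume.** V = CL × 24 × T / ln 2.
- IV: 0.016 × 24 × 15.4 / 0.693 = 8.53 L.
- SC (V/F): 0.029 × 24 × 16.6 / 0.693 = 16.67 L.

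**Concentration.** C(t) = dose × weight / V × 2^(−t/T), with V held constant when T is doubled. Example at 40 mg/kg IV, day 28: 40 × 70 / 8.53 × 2^(−28/15.4) = 93 mcg/mL, and with T = 30.8 days, 175 mcg/mL.

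| Dose, 70 kg | Week 4 (mcg/mL) | 12 weeks after dose | 24 weeks after dose |
|---|---|---|---|
| 1 mg/kg IV | 2.3-4.4 | 0.19-1.24 | up to 0.19 |
| 5 mg/kg SC | 6.5-11.7 | 0.63-3.64 | 0.02-0.63 |
| 5 mg/kg IV | 11.6-21.9 | 0.94-6.2 | 0.02-0.94 |
| 20 mg/kg IV | 46.5-87.4 | 3.7-24.8 | 0.09-3.7 |
| 40 mg/kg IV | 93-175 | 7.5-49.6 | 0.17-7.5 |

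These are single-dose values; accumulation by the third dose adds about 2 to 20%. For the same clearance and half-life, a two-compartment drug would lie at or below them in the terminal phase.

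**Sensitivity.** At 40 mg/kg, week 4 is 67-125 mcg/mL at 50 kg and 153-287 at 115 kg. Varying VRC01 clearance and half-life by one SD at 70 kg gives 68-118.

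**Macaque cross-check.** Section 2.4, Table 2 gives 114.2 mcg/mL at day 5 after 20 mg/kg IV. Decaying this 23 days at half-lives of 9.8 to 14 days gives 114.2 × 2^(−23/9.8) = 22 to 114.2 × 2^(−23/14) = 37 at 20 mg/kg. Scaled by dose, that is 45-73 at 40 mg/kg and 1.1-1.8 at 1 mg/kg.

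**Dose gradient.** Under linear PK the 1 to 40 mg/kg IV ratio is 40-fold, whichever half-life, volume or weight is used.

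**Gain from a later sample (IV).** Week 4 to week 24: 2^(140/30.8) = 23-fold to 2^(140/15.4) = 545-fold. Week 4 to week 12: 2^(56/30.8) = 3.5-fold to 2^(56/15.4) = 12-fold.

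**What masking would do, if it occurred.** Take a true ADA rate of 20% and n = 5. The zero-event column of Table 4 gives the chance of at least one detected positive:
- no masking: 1 − 0.328 = 0.67
- half masked (effective rate 0.1): 1 − 0.590 = 0.41
- three quarters masked (effective rate 0.05): 1 − 0.774 = 0.23

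The masking fractions are illustrative; the documents support no particular value.

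**The case against.** The best reply is that the plan already allows other visits to be tested. ADA that speeds clearance lowers the PK profile, which permits further testing, and the lower drug level also reduces the interference. That part stands. However, the sentence is permissive, sets no threshold for a PK decrease, and does not reach masked ADA that produces neither sign. It also gives no criterion for a valid negative.

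Second, the assay description is a summary. The PK ELISA is set out step by step, while the ADA assay is reduced to platform, capture and reporter. A reader might infer that the method has no dissociation step; silence in so short an account does not show that. Tolerance and pre-treatment may be in assay documents not seen here. If tolerance exceeds about 175 mcg/mL, no group is affected at 70 kg under these assumptions. This also stands, and it limits the point to a risk.

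Third, the study is descriptive, Section 6.4 plans no ADA comparison across doses, and with 3 to 5 subjects per group a dose trend could hardly be read in any case (Table 5: 0/3 has an upper bound of 0.708). That is fair, but the objective also depends on whether each individual negative can be believed.

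Fourth, a later sample may still hold too much drug: 12 weeks after 20 mg/kg the range is 3.7-24.8 mcg/mL. This is correct, and the rule below has to provide for it.

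**Conclusion.** The point holds as a risk that is cheap to remove. The assay is a bridging format, the only routine samples are at 4 weeks, and drug is then extrapolated at roughly 2 to 175 mcg/mL depending on dose. A week-4 negative may therefore be masked ADA, and the risk rises with dose. The absolute levels rest on VRC01 kinetics, a 1- to 2-fold half-life and 70 kg; macaque-anchored levels are lower. The gradient needs only linear PK.

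Two stronger readings are not supported. A reader might infer that all groups hold tens to hundreds of mcg/mL at week 4. That does not fit 1 mg/kg IV, and 5 mg/kg SC (about 7-12) is borderline at best; together these are Groups 1, 3 and 6, 11 of the 25 planned subjects. At 70 kg, levels above 100 arise only at 40 mg/kg, and only if the half-life is longer than, or clearance lower than, the VRC01 mean. A reader might also infer that the observed ADA rate must fall with dose. That would require a tolerance below the high-dose levels, and the documents give no tolerance.

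**What to change.** In Sections 1.2 and 6.4:

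- **Add a routine low-drug sample for every subject.** Keep the 4-week test and add the serum already scheduled 24 weeks after the last dose. In Groups 6 and 7, also add the pre-dose draws at weeks 12 and 24.
- **Report each ADA result with the VRC07-523LS concentration from the same visit.** Appendix III schedules PK and serum tubes at these visits. The PK standard curve starts at 0.98 ng/mL and the lowest sample dilution is 100, so levels down to about 0.98 × 100 = 98 ng/mL (0.1 mcg/mL) in serum can be read.
- **Define a valid negative.** Count a sample as ADA-negative only if its drug concentration is within the assay's validated tolerance, and state that tolerance. Otherwise report it as not evaluable, including when the late sample also exceeds tolerance. Show the number evaluable as the denominator.

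The cost is a wording change and a few extra batch runs on stored serum, with no new visit or blood draw. The downside is that fewer results may count as negative at high doses. If the tolerance proves to be above the measured levels, no result is reclassified.
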